**Statistical Methods:**

Study Populations

**Safety Population:** Safety analyses will be performed on the Safety Population defined as all subjects who receive at least one dose of ZX008 during the open label extension.

**Modified Intent-to-Treat (mITT) Population:** The mITT Population is defined as all subjects who receive at least one dose of ZX008 and have valid seizure data during the open label extension.

Safety

The number and percentage of subjects who experience treatment emergent AEs will be displayed by body system and preferred term using the Medical Dictionary for Regulatory Activities (MedDRA). Summaries in terms of severity and relationship to study drug will also be provided. Serious AEs

(SAEs) will be summarized separately in a similar manner. Laboratory tests, vital signs, physical examinations, neurological examinations, ECG, ECHO, cognition and body weight will be summarized using appropriate methods.

#### Effectiveness

The frequency of convulsive seizures during a given treatment period will be derived from the number and type of events recorded in subject diaries. The seizure frequency per 28 days will be calculated as the number of seizures recorded divided by the number of days in the period and multiplied by 28. The convulsive seizure frequency during the OLE Treatment Period will be compared to the pre-ZX008 baseline frequency measured prior to first treatment with ZX008. Both the mean and median change from baseline will be presented and the statistical significance of the change will be assessed using an analysis of covariance (ANCOVA) with baseline frequency as a covariate and age group ( $\leq 6$  or  $\geq 6$  years old) as a factor. Other factors may be included in the model if they are found to be informative during analyses of the core trials. Similar methods will be used to assess the change in frequency of non-convulsive seizures and the composite endpoint of non-convulsive plus convulsive seizures. The percentage of subjects who achieve a  $\geq 40\%$ ,  $\geq 50\%$ , and  $\geq 75\%$  reduction in seizures will be presented along 95% confidence intervals for each percentage. Quality of life measures, such as the QOLCE assessed during the OLE Treatment Period, will be compared to the analogous baseline measure assessed prior to first treatment with ZX008. Subjects who did not participate in one of the core studies will be excluded from analyses of effectiveness and the change over time will be described.

**Table 1. Schedule of Assessments for Subjects from Core Studies ZX008-1501 and ZX008-1502, and de Novo Subjects\*\***

Study Assessments	OLE Treatment Period				Post-Dosing Visit 17 o	Cardiac Follow-up Visit 18, 19 o	
	Visit 1 a	Visit 2 c		Visits 3-15 (Months 1, 2, 3, 6, 9, 12, 15, 18, 21, 24, 27, 30, and 33)			Visit 16 d (EOS/ET) Month 36
Study Day	-28 to 1 a	15		30, 60, 90, 180, 270, 365, 455, 545, 635, 725, 815, 905, 995	1085	1099	3 and 6 months post last dose
		Clinic	Phone				
Informed Consent	X						
Entry Criteria	X						
Demographics	X						
Medical/Neurological History	X a						
Epilepsy History	X a,b						
Physical Examination, complete	X a				X		X e
Physical Examination, abbreviated		X		X			X e
Neurological Examination, complete	X f				X		
Neurological Examination, abbreviated		X		X			
Vital signs	X	X		X	X		
Weight, Height, BMI	X a	X		X	X		
12-lead ECG	X a			X	X		X e
Doppler ECHO	X a			X g,h	X		X e
Urine Pregnancy Test h	X			X	X		
Clinical laboratory evaluation (hematology/clinical chemistry/urinalysis, etc)	X j	X j		X	X		
Urine THC Panel/Whole blood CBD	X a			X	X		
Plasma sample for background AEDs		X		X	X		
Tanner Staging (for subjects >7 to ≤ 18 years)	X a			X k	X		X k
C-SSRS	X a			X	X		
CGI-I (assessed by parent/caregiver)	X a			X	X		
CGI-I (assessed by principal investigator)	X a			X	X		
QOLCE	X a			X	X		
EQ-5D-5L (QoL of parent/caregiver)	X a			X	X		
HADS (Affect of parent/caregiver)	X a			X	X		
BRIEF	X a			X	X		

*continued*

**Table 1. Schedule of Assessments for Subjects from Core Studies ZX008-1501 and ZX008-1502, and de Novo Subjects\*\* (continued)**

Study Assessments	OLE Treatment Period				Post-Dosing	Cardiac Follow-up	
	Visit 1 a	Visit 2 c		Visits 3-15 (Months 1, 2, 3, 6, 9, 12, 15, 18, 21, 24, 27, 30, and 33)	Visit 16 c (EOS/ET) Month 36	Visit 17 o	Visit 18, 19 o
Study Day	-28 to 1 a	15		30, 60, 90, 180, 270, 365, 455, 545, 635, 725, 815, 905, 995	1085	1099	3 and 6 months post last dose
PedsQL n	X a	Clinic	Phone	X	X		
Study medication palatability assessment				X l			
Subject Diary	D	C/R/D	R	C/R/D	C/R	C/R	
Study Medication	D b	C/R/D	R	C/R/D	C/R/D	C/R	
Daily Diary Completion		-----X-----					
Concomitant Medication	X a	-----X-----					
Adverse Events	X a	-----X-----					
Adverse events of special interest	X a	-----X-----					X m

AED=antiepileptic drug; BMI=body mass index; BRIEF=Behavior Rating Inventory of Executive Function; C=Collect; CBD=cannabidiol; CGI-I=Clinical Global Impression-Improvement; D=Dispense; ECG=electrocardiogram; EOS=end of study; ET=early termination; EQ-5D-5L=standardized measure of health status; HADS=Hospital Anxiety and Depression Scale; PedsQL=Pediatric Quality of Life Inventory; QoL=quality of life; QOLCE=Quality of Life in Childhood Epilepsy; R=Review

**NOTE: If a subject has a birthday during the study that makes a previously unrequired assessment now required (eg, Tanner staging in a male subject who turns 8 years old during the study), this assessment(s) should be initiated at visits subsequent to the birthday.**

**\*\* de Novo subjects are subjects who did not participate in one of the core studies and may or may not be currently taking STP.**

- a: For subjects enrolling from one of the core studies use data collected at Visit 12 and Visit 13 of Study ZX008-1501 or ZX008-1502. For de novo subjects, a screening period up to 28 days is required. During this period, informed consent is required prior to any study-related procedures. All results to determine eligibility must be reviewed prior to receiving the first dose of study medication at Visit 1. For all subjects, clinical laboratory results and all ECHO/ECG results must be available and meet eligibility criteria prior to receiving the first dose of study medication at Visit 1.
- b: De Novo subjects must meet entry criteria 3 to 7, and 10, including having had ≥4 convulsive seizures (tonic, tonic-atonic, tonic-clonic, clonic) per 4-week period for past 12 weeks prior to screening, by parent/guardian report to investigator or investigator medical notes.
- c: At the discretion of the investigator, Visit 2 may be conducted as a phone visit.
- d: Or early termination.
- e: Follow-up ECG, ECHO, and physical examination will be performed 3 and 6 months after study completion or early termination (see Section 6.3).
- f: For subjects enrolling from one of the core studies, use core study Visit 12 information unless complete neurological examination is warranted based on significant changes in subject status.
- g: ECHOs will be performed at Months 1, 3, 6, 9, 12, 15, 18, 21, 24, 27, 30, and 33.
- h: The Months 3, 6, 9, 12, 15, 18, 21, 24, 27, 30, and 33 ECHO may be performed any time within 3 weeks prior to the study visit. If a subject discontinues early from the study, the ECHO should be scheduled as soon as practical (see Table 7).
- i: Females of child-bearing potential
- j: For subjects enrolling from one of the core studies, use data collected at Visit 12 of ZX008-1501 or ZX008-1502 for Visit 1 unless clinical laboratory evaluation is warranted based on significant changes in subject status. Visit 2 clinical laboratory evaluation is optional based on subject status for all cohorts.
- k: Visits 6, 15, and 27 only.
- l: Visits 3 and 4 (Months 1 and 2) only.
- m: Only adverse events related to cardiac safety will be collected at this visit (see Table 7).
- n: Not to be completed for de novo subjects >18 years old.
- o: For subjects who are entering the separate extension trial or who transition to commercially available drug, post-dosing and cardiac safety follow-up visits are not required in this trial.

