- b: At the discretion of the investigator, Visit 2 may be conducted as a phone visit.
- c: Or early termination.
- d: Follow-up ECG, ECHO, and physical examination will be performed 3 and 6 months after study completion or early termination (see Section 6.3).
- e: Unless complete neurological examination is warranted based on significant changes in subject status, use data collected at the last visit of the transition period of Study ZX008-1504 Cohort 1 and for subjects from Study ZX008-1504 Cohort 2, use data collected at the Visit 12.
- f: ECHOs will be performed at Months 1, 3, 6, 9, 12, 15, 18, 21, 24, 27, 30, and 33.
- g: The Months 3, 6, 9, 12, 15, 18, 21, 24, 27, 30, and 33 ECHO may be performed any time within 3 weeks prior to the study visit. If a subject discontinues early from the study, the ECHO should be scheduled as soon as practical (see Table 7).
- h: Females of child-bearing potential
- i: Unless clinical laboratory evaluation is warranted based on significant changes in subject status, use data collected at the last visit of the transition period of Study ZX008-1504 Cohort 1; for subjects from Study ZX008-1504 Cohort 2, use data collected at the Visit 12. For Visit 2, clinical laboratory evaluation is optional based on subject status.
- j: Visits 6, 15, and 27.
- k: Visits 3 and 4 (Months 1 and 2) only.
- l: Only adverse events related to cardiac safety will be collected at this visit (see Table 7).
- m: For subjects who are entering the separate extension trial or who transition to commercially available drug, post-dosing and cardiac safety follow-up visits are not required in this trial.

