After at least 1 year of treatment in Study 1503 subjects who participated in one of the core studies will transition to a separate extension study (Study 1900) once that study is approved and the study site is initiated. Continuation in a separate extension protocol will be based on benefit/risk and continued eligibility criteria being met. De novo subjects must have participated in this trial for at least 3 months with at least 1 ECHO completed and continue to meet eligibility requirements to be eligible to transition to a separate extension protocol. Alternatively, subjects will transition to commercial product once it is available. For subjects who are entering the separate extension trial or who transition to commercially available drug, post-dosing and cardiac safety follow-up visits are not required in this trial. Subjects who transition to commercially available drug must have an ECHO within 3-6 months before starting commercial drug and will have follow-up ECHOs within the required timeframe while on commercial drug.

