## 5.4 TREATMENT ADMINISTRATION

### 5.4.1 OLE Treatment Period

The investigator (or delegate) will dispense IMP only to subjects included in this study following the procedures set out in this study protocol.

Study medication will be administered as equal doses BID in the morning and in the evening, approximately 12 hours apart, with food. Each dose should be separated by a minimum of 8 hours and a maximum of 12 hours. A missed dose of study medication may be taken later up to 8 hours before the next scheduled dose; otherwise, the missed dose should not be given. Administration of the initial IMP will be based on the 0.2 mg/kg/day (maximum 30 mg/day or

20 mg/day for subjects taking concomitant STP) dose and subject's weight at Visit 1 (Study Day 1). At Visits 5 to 15 (Months 3 to 33), if the subject's weight has changed  $\pm 25\%$  of the weight from the previous dose calculation, the IMP dose will be recalculated. Subjects will be dosed using the oral dosing syringe provided.

During the OLE Treatment Period, all subjects will be treated initially with 0.2 mg/kg/day for 1 month to assess effectiveness of this dose in all study subjects. After 1 month at a dose of ZX008 0.2 mg/kg/day, the investigator may adjust the dose of each subject based on effectiveness and tolerability.

Dose changes should be made in increments of 0.2 mg/kg/day, as follows:

- Subjects who are not receiving concomitant STP: may increase to a maximum of 0.8 mg/kg/day but not to exceed total dose of 30 mg/day
- Subjects who are receiving concomitant STP: the first dose change will be to 0.4 mg/kg/day and the final dose change will be to 0.5 mg/kg/day, but not to exceed 20 mg/day

Dose increases should not occur earlier than every 14 days at each dose level. Dose increases may only occur after a review of the diary and reported AEs, and if, in the investigator's opinion, seizure frequency, severity, and/or duration indicates a change in medication regimen is warranted. Dose decreases for tolerability can occur at the investigator's discretion, in dose amounts and frequency appropriate for the situation. ZX008 dose adjustments outside of these parameters should be discussed with the Medical Monitor prior to initiation.

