**Table 7. Time Windows for Assessments**

Visit / Procedure	Time window (relative to scheduled visit / procedure)
Visit 1 (Clinic; Study Day 1)	Not applicable (this is the same visit as Visit 13 from the core study)
Visits 2 (Clinic/Phone; Study Day 15)	± 3 days
Visits 3-15 (Clinic; Study Days 30, 60, 90, 180, 270, 365, 455, 545, 635, 725, 815, 905, 995)	± 4 days
Visit 16 (Clinic; Study Day 1085)	± 4 days
Visit 17 (Clinic; Study Day 1099; post dosing)	± 4 days
Visit 18, 19 (ECHO clinic; 3 and 6 months after last dose)	+ 30 days
Blood collection for AED concentration	Prior to morning dose of AED medication

AED=antiepileptic drug (s); ECHO=echocardiogram

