#### 6.1.4 Clinic Visits 3-15 (Months, 1, 2, 3, 6, 9, 12, 15, 18, 21, 24, 27, 30, 33)

Subjects will report to the clinic in the morning of Clinic Visits 3 through 15. Subjects should not take their morning dose(s) of AED prior to reporting to the clinic. The following procedures will be performed:

- Review current seizure activity (number/type/duration) from diary since previous visit
- Record concomitant medications
- Abbreviated physical examination, including height and weight, and calculation of BMI
- Abbreviated neurological examination
- Obtain vital signs
- 12-lead ECG
- Doppler ECHO (at Months 1, 3, 6, 9, 12, 15, 18, 21, 24, 27, 30, 33)
- Urine pregnancy test for females of child-bearing potential
- Laboratory evaluation (serum chemistry and hematology, and urinalysis)
- Urine THC panel
- Whole blood CBD
- Collect plasma sample for AED PK evaluation prior to the morning dose of study medication(s)
- Tanner Staging for subjects > 7 to ≤18 years of age (Visits 6, 15, and 27 only) ([Appendix 5](#))
- Collect and review diary with parent/caregiver
- Dispense diary
- C-SSRS Children's Since Last Visit Assessment ([Appendix 2](#))
- CGI-I (assessed by parent/caregiver)
- CGI-I (assessed by investigator)
- BRIEF ([Appendix 3](#))
- QOLCE ([Appendix 4](#))
- PedsQL ([Appendix 6](#)) (only for subjects from the core studies)
- Parent/Caregiver QoL using the EQ-5D-5L scale ([Appendix 7](#))
- Affective symptoms of parent/caregiver using the HADS scale ([Appendix 8](#)) (for subjects from core studies ZX008-1501 and ZX008-1502 only)
- Healthcare utilization questions (for subjects from core study ZX008-1504 only)
- Karolinska Sleepiness Scale ([Appendix 10](#)) (for subjects from core study ZX008-1504 only)

- Sleep quality and mealtime behavior questions (for subjects from core study ZX008-1504 only)
- Study medication palatability assessment (Visits 3 and 4 only)
- Record AEs
- Record AESI
- Collect used, partially used and unused study medication; perform drug accountability and review with parent/caregiver
- Dispense study medication

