### **7.3.9 Tanner Staging**

Tanner Staging ([Appendix 5](#)) will be assessed for subjects >7 years old during the study as outlined in [Table 1](#) and [Table 2](#). Conceptually, pubertal maturation can be described in terms of sequence, timing, and tempo. Puberty consists of a series of predictable events, and the sequence of changes in secondary sexual characteristics has been categorized by several groups. The staging system used most frequently was published by Marshall and Tanner (1969, 1970) and the sequence of changes are commonly referred to as 'Tanner stages'.

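### Tanner staging is scheduled at Visits 6, 15 and 27, but there is no Visit 27 and Visit 15 is Month 33; months were very probably meant

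*Protocol*

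**What the plan says.** Three places in the current text fix the timing of Tanner staging during treatment:

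- Table 1, footnote k: "Visits 6, 15, and 27 only".
- Table 2, footnote j: "Visits 6, 15, and 27", without the restricting word.
- Section 6.1.4, in its list of procedures, repeats the three visit numbers and does include the restriction.

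Section 7.3.9 adds no timing of its own. It says that staging "will be assessed for subjects >7 years old during the study as outlined in" Tables 1 and 2.

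The visit numbering is set elsewhere. The heading of Section 6.1.4 reads "Clinic Visits 3-15 (Months, 1, 2, 3, 6, 9, 12, 15, 18, 21, 24, 27, 30, 33". Section 5.4.1 fixes both ends of most of that range: "At Visits 5 to 15 (Months 3 to 33". The last line of Table 7 that carries visit numbers is "Visit 18, 19 (ECHO clinic; 3 and 6 months after last dose". Visit 16 is the Month 36 end-of-study or early-termination visit, and Visit 17 is the post-dosing visit.

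Staging is also required at Visit 1 (core-study data may be used) and at Visit 16.

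**The concern.** One of the three listed visits cannot take place, and a second falls at a month that does not look intended. Visits 6 and 15 are real visits, so a site can follow the line as written, ignore only the impossible entry, and not notice that anything is wrong. It would then stage at Month 33 and omit Months 15 and 27.

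What is at stake is how often pubertal development is observed in children and adolescents on long-term treatment. Tanner staging is one of the protocol's safety assessments, and the laboratory panel contains a group of tests for growth and precocious puberty (Section 7.3.5), so the subject was deliberately included. A child who passes the age threshold after Month 6 could, on the literal schedule, be staged first at Month 33 or at exit.

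There is a secondary mismatch. The Tanner row has a mark in the cardiac follow-up column (Visits 18 and 19) of both tables, whereas Section 6.3 lists only echocardiography, ECG and, in some cases, physical examination at those visits.

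**Working it through.** **Inputs.** Visits 3 to 15 are 13 visits. Table 1, Table 2 and Section 6.1.4 list 13 months for them, and the tables list 13 study days, so they pair one to one:

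| Visit | 3 | 4 | 5 | 6 | 7 | 8 | 9 | 10 | 11 | 12 | 13 | 14 | 15 |
|---|---|---|---|---|---|---|---|---|---|---|---|---|---|
| Month | 1 | 2 | 3 | 6 | 9 | 12 | 15 | 18 | 21 | 24 | 27 | 30 | 33 |
| Day | 30 | 60 | 90 | 180 | 270 | 365 | 455 | 545 | 635 | 725 | 815 | 905 | 995 |

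Two statements confirm the pairing. Section 5.4.1 puts Visit 5 at Month 3 and Visit 15 at Month 33, and Section 2.2 puts Visit 8 at Day 365. Visit 16 is Month 36, Day 1085.

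**Lookup.**

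- As visit numbers: Visit 6 = Month 6 (Day 180), Visit 15 = Month 33 (Day 995), Visit 27 = not defined.
- As months: Month 6 = Visit 6 (Day 180), Month 15 = Visit 9 (Day 455), Month 27 = Visit 13 (Day 815). All three are scheduled visits.

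**Longest gap between stagings.** Let T be the month of exit, with staging at Visit 1 (Month 0) and at exit.

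- Literal reading: stagings at Months 0, 6, 33 and T. The longest gap is T − 6 for T from 12 to 33, and 33 − 6 = 27 for T = 36.
- Month reading: stagings at Months 0, 6, 15, 27 and T. The longest gap is 6 for T = 12, 15 − 6 = 9 for T = 15 to 24, and 27 − 15 = 12 for T = 27 to 36.

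| Exit month | Literal (months) | Month reading (months) |
|---|---|---|
| 12 | 6 | 6 |
| 15 | 9 | 9 |
| 18 | 12 | 9 |
| 21 | 15 | 9 |
| 24 | 18 | 9 |
| 27 | 21 | 12 |
| 30 | 24 | 12 |
| 33 or 36 | 27 | 12 |

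In days, for a 36-month stay:

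- Literal: the longest gap is 995 − 180 = 815.
- Month reading: the gaps after Day 180 are 455 − 180 = 275, 815 − 455 = 360 and 1085 − 815 = 270, so the longest is 360.

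**Number of stagings.**

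- Exit at Month 36: 4 on the literal reading (Days 1, 180, 995, 1085) and 5 on the month reading (Days 1, 180, 455, 815, 1085).
- Exit at Month 30: 3 (Months 0, 6, 30) and 5 (Months 0, 6, 15, 27, 30).

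**The case against.** The strongest reply is that this is a labelling slip with little consequence. Tanner stage is not a listed safety endpoint (Section 2.4.2), not an adverse event of special interest (Table 10) and not a reason for discontinuation (Section 4.4), and Section 10.5.1 names no analysis of it. Hormones, height and weight are measured at each clinic visit from Day 30, and anyone leaving early is staged at the exit visit. All of that stands and limits the weight of the point.

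The 27-month gap is also a worst case. It needs a long stay and a site that takes the visit numbers at face value. Section 3.1 states: "After at least 1 year of treatment in Study 1503 subjects who participated in one of the core studies will transition" to Study 1900 once that study is approved and the site is initiated, or else to commercial product. De novo subjects are over 18 and so outside the age range given in Table 1. The protocol does not say how many subjects stay beyond Month 15, so the practical reach is unknown. Stays of that length do occur, however: Section 1.3 reports interim seizure data through Month 24, and Section 1.10 mentions participation of up to 3 years.

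Some text softens the restriction. Footnote j in Table 2 does not limit staging to the named visits. A note under both tables starts newly required assessments at visits after the relevant birthday. The COVID-19 appendix includes Tanner staging among the items for remote visits where applicable and feasible. None of these supplies the missing visit or states which months were intended.

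On the secondary point, the mark in the cardiac column appears to carry the same footnote, which does not list Visits 18 or 19. Read strictly, nothing is then required there, in agreement with Section 6.3. It is best treated as a stray mark to tidy up.

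**Conclusion.** The schedule is wrong as written. It names a visit that does not exist in three places, and read literally it puts another staging at Month 33. The longest interval between stagings is 27 months instead of 12 for subjects who stay to Month 33 or 36, 18 instead of 9 for an exit at Month 24, and 12 instead of 9 at Month 18. There is no difference up to Month 15.

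These figures assume staging at Visit 1 and at exit, and a site that omits only the impossible visit. That months were meant is an inference. It is a strong one, because 6, 15 and 27 are all in the month list and the resulting visits are fairly evenly spaced, but only the sponsor can confirm it.

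The effect is confined to the timing of one pubertal-development assessment in subjects in the staging age range who stay past Month 15. It should be corrected, but no conclusion on efficacy or sample size depends on it.

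**What to change.** Ask the sponsor to confirm the intended timing. If months were meant, change Table 1 footnote k, Table 2 footnote j and Section 6.1.4 to: Visits 6, 9, and 13 (Months 6, 15, and 27) only. That gives visit numbers together with months, as Table 1 footnote l already does for palatability: "Visits 3 and 4 (Months 1 and 2) only".

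At the same time, reconcile the Tanner mark in the cardiac follow-up column of both tables with Section 6.3, either by removing the mark from both tables or by adding Tanner staging to that section.

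The cost is three text corrections and one mark in each of two tables at the next amendment, plus a memo to sites. No visit is added. Compared with the literal schedule, a subject who stays 36 months has one more staging, and one who leaves at Month 30 has two more. All of them fall at visits already planned.
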